## 7 Summary of study data

---

All continuous variables will be summarized using the following descriptive statistics: n (non-missing sample size), mean, standard deviation, median, and intra-quartile range. The frequency and percentages (based on the non-missing sample size) of observed levels will be reported for all categorical measures. All summary tables will be structured with a column for each study arm and will be annotated with the total population size relevant to that table/treatment, including any missing observations.

### 7.1 Trial Profiles

#### 7.1.1 Intervention

The overall study profile for the intervention will be presented as a figure following CONSORT guidelines. This will include the number of clusters allocated to the 2 treatment arms, the estimated number of household targeted for the intervention in the sub-county surrounding each MRC, the estimated number of households in the target area where the outcomes will be assessed, and the estimated population of the target area where the outcomes will be assessed.

#### 7.1.2 Community surveys

For the community surveys additional flow diagrams will detail participation in the survey, including the number of households recruited and screened, reasons for exclusion, and number of households enrolled. The figure will include details of the number of children aged 2-10 years recruited and screened for the clinical survey, reasons for exclusion, number of children included, and the number with complete data included in the analysis.

### 7.2 Characteristics of clusters, households, and residents

The baseline characteristics of the clusters from the enumeration surveys and characteristics of the households and residents assessed at the time of the 12 and 24 month cross-sectional surveys will be presented by study arm. For continuous variables the mean and standard deviation will be presented. For skewed continuous variables, either geometric mean or the median and inter-quartile range will be presented, and for categorical variables the number and percentage in each category.

## 8 Efficacy analyses

---

### 8.1 Primary outcome

The primary outcome of the study will be the cumulative incidence of malaria over the 24 month follow-up period. The total number of cases of malaria for each MRC target area will be the number of laboratory confirmed cases of malaria from patients who report residing in the target area over the 24 month follow-up period, with two correction factors: 1) for patients who reside within the target area with suspected malaria who do not undergo laboratory testing, and 2) for patients with laboratory confirmed malaria whose village of residence is missing. The population of the MRC target area will be used for incidence calculations.

#### 8.1.1 Analytical approach

All analyses will be conducted using an intention-to-treat approach according to the treatment allocations the clusters were randomized to. We will compare cluster level estimates of the incidence of malaria

between the intervention (PPF LLINs) and control arm (PBO LLINs) using a mixed effects Poisson regression model with a random effect at the district level (each district includes two clusters, randomized to one of the two study arms) and adjustment for log-transformed estimates of the baseline malaria incidence (3 months prior to the intervention) for each cluster. The effect of the intervention will be expressed as an incidence rate ratio (incidence in the intervention arm/incidence in the control arm). Our primary analysis will evaluate malaria incidence over 24 months following the intervention. We will also perform secondary analyses of malaria incidence stratified by time following the intervention (year 1 vs. year 2) and after adjusting for additional cluster-level covariates from the cross-sectional surveys including treatment seeking behaviour (to account for cases of malaria not captured at the MRCs) and the diagnostic accuracy of RDTs vs microscopy (to account for differences in the use of these diagnostic tests between clusters). These models will include random effects at the cluster level and we will assess the need for an additional random effect at the District level.

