### 3.1 General study design and plan

We propose to conduct a rigorous, cluster-randomised trial to evaluate the impact of LLINs distributed in Uganda through the 2020-21 national universal coverage campaign. A cluster has been defined as the target area of an MRC. A total of 64 clusters have been included in the study, covering 32 high malaria burden districts in Uganda where IRS is not being implemented. Clusters have been randomised in a 1:1 ratio in blocks of two by district to receive one of two types of LLINs: (1) PPF LLINs (Royal Guard [n=32] and (2) PBO LLINs (PermaNet 3.0) [n=32] (Appendix A).

The intervention, including delivery of the LLINs and social and behaviour change communication (SBCC), will be led by the Ugandan NMCD and other stakeholders. Currently, LLINs are scheduled to be delivered in the study areas from November 2020 to March 2021. The evaluation will include health facility surveillance at the MRCs to generate continuous estimates of malaria incidence for each MRC target area and cross-sectional community surveys at 12- and 24-months after LLIN distribution to gather information on net ownership and use, parasite prevalence in children 2-10 years of age, and anemia in children 2-4 years of age.

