### 3.2 Cluster definition

The unit of randomisation (cluster) was the target area around each MRC; 64 MRCs from 32 districts were included. Target areas around the MRCs were identified before LLINs were distributed and included the village where the MRC is located and adjacent villages that meet all of the following criteria: 1) do not contain another health facility, 2) are within the same sub-county as the village where the MRC is located, 3)

have a similar incidence of malaria as the village where the MRC is located, and 4) provide an estimated total target area population of at least 1200 persons.

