### 3.3 Cluster randomisation

Given the open-label study design and the need to generate estimates of the targeted number of LLINs for distribution in advance, randomisation was completed at the time of the protocol development. The randomisation was carried out by a member of the study team who is not based in Uganda and not directly involved in the field work. The unit of randomisation (cluster) was at the level of the MRC and the surrounding sub-county targeted for LLIN distribution. Randomization was done in blocks of 2, with each block representing a district containing 2 clusters with one cluster assigned the letter "A" and one cluster assigned the letter "B". For each block, a random number between 0 and 1 was generated using the 'runiform' command in STATA (StataCorp, Texas, USA). If the random number was  $<0.5$ , cluster "A" was assigned to PBO LLINs and cluster "B" was assigned PPF LLINs. If the random number was  $\geq0.5$ , cluster "A" was assigned to PPF LLINs and cluster "B" was assigned PBO LLINs. The final treatment allocations are summarized in Table 1, and the full intervention allocation list is provided in Appendix A.

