## **6.1 Primary outcome**

Our sample size of 32 clusters per arm was calculated to detect a 26% decrease (incidence rate ratio (IRR) = 0.74) in the incidence of malaria over the 24 month period following the intervention (the primary endpoint of the study) between the two study arms, given a power of 80% and a two-sided significance level of 0.05. This sample size calculation assumes an incidence of 332 malaria cases per 1000 person-years in the control arm and a coefficient of variation (CV) of 0.42 calculated from the 14 MRCs where estimates of malaria incidence are available over the last 6 month at the time of protocol development.

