### 8.2.1 Analytical approach

All analyses will be conducted using an intention-to-treat approach according to the treatment allocations the clusters were randomized to. Separate analyses will be conducted for the 12 and 24 month cross-sectional surveys. We will compare individual level estimates of the prevalence of parasitemia and anemia between the intervention (PPF LLINs) and control arm (PBO LLINs) using a mixed effects logistic regression model with random effects at the level of the cluster and household. We will compare household level estimates of LLIN ownership, coverage, and use using a mixed effects logistic regression model with a random effect at the level of the cluster. Effects of the intervention will be expressed as odds ratios (odds in the intervention arm/odds in the control arm).

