### 9.2 Covariates

In the primary analysis of the primary outcome (malaria incidence) we will adjust for cluster level baseline estimates of malaria incidence (3 months prior to the intervention). In secondary analyses of the primary outcome we will adjust for additional cluster-level covariates from the cross-sectional surveys including treatment seeking behaviour (to account for cases of malaria not captured at the MRCs) and the diagnostic accuracy of RDTs vs microscopy (to account for differences in the use of these diagnostic tests between clusters).

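### The primary Poisson model in SAP 8.1.1 has no cluster-level variance term, so its nominal 5% test can reject a true null far too often

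*SAP*

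**What the plan says.** Randomisation is paired: "Clusters have been randomised in a 1:1 ratio in blocks of two by district", and SAP 3.3 confirms that "The unit of randomisation (cluster) was at the level of the MRC and the surrounding sub-county". Each of the 32 districts therefore supplies one PPF cluster and one PBO cluster.

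For the primary outcome, SAP 8.1.1 compares cluster-level incidence "using a mixed effects Poisson regression model with a random effect at the district level", with log baseline incidence over three months as the covariate. It then describes secondary analyses (year 1 against year 2, and added survey covariates) and closes with "These models will include random effects at the cluster level and we will assess the need for an additional random effect" at district level.

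SAP 9.2 draws the same line between the two sets of analyses: the primary one adjusts for baseline incidence only, and "In secondary analyses of the primary outcome we will adjust for additional cluster-level covariates from the cross-sectional surveys". Protocol 13.5 also names a mixed effects Poisson model, but not the level of its random effect.

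For parasitaemia and anaemia, SAP 8.2.1 does state the cluster term: "using a mixed effects logistic regression model with random effects at the level of the cluster and household". It also gives a cluster effect for net ownership, coverage and use. The sample size in SAP 6.1 rests on "a coefficient of variation (CV) of 0.42 calculated from the 14 MRCs".

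**The concern.** A district random effect absorbs what the two clusters of a pair share. The arm contrast is the difference within the pair, so that effect cancels. In a Poisson model with no further variance term, the two clusters of a district may then differ only through net type, measured baseline incidence and counting error.

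The plan gives reasons to expect more variation than that:
- The trial was sized on a between-cluster CV of 0.42.
- The secondary models adjust for care seeking and for the mix of diagnostic tests, because these may differ between clusters.
- In the Protocol's Table 2, 19 of the 32 districts pair a level IV with a level III health centre.

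If such variation is left out, the primary confidence interval is too narrow and the p-value too small. A chance difference between neighbouring target areas could be reported as an effect of net type, in either direction.

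**Working it through.** **Inputs from the documents.** Control incidence is 0.332 per person-year, follow-up 2 years, CV 0.42, IRR 0.74, 32 clusters per arm, two-sided 5% and 80% power (SAP 6.1). The minimum target-area population is 1,200 (SAP 3.2) or 1,500 (Protocol 13.2).

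**Assumed input.** s is the SD of the log rate between a district's two clusters that remains after baseline adjustment and counting error. The documents do not give it, so a range is shown.

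**1. The plan's own figure.** Use the unmatched rate formula c = (1.96 + 0.842)² × [(λ0 + λ1)/y + CV²(λ0² + λ1²)] / (λ0 − λ1)², with λ0 = 0.332, λ1 = 0.74 × 0.332 = 0.2457 and y = 2,400 person-years. The bracket is 0.00024 + 0.03009 = 0.03033 and the denominator is 0.00745, so c = 31.95. The stated 32 per arm is reproduced. Almost all of the bracket is between-cluster variance, not counting error.

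**2. What the primary model allows for.** Expected cases per cluster are μ = 0.332 × 2 × 1,200 = 797, or 996 at 1,500. Counting error is 1/√μ = 3.5% or 3.2%. With 32 pairs, the model SE of the log IRR is √(2/(32μ)) = 0.0089 or 0.0079.

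**3. What is true if s > 0.** The variance per pair is 2/μ + 2s², but the model uses 2/μ. The test statistic is inflated by R = √(1 + μs²), and the type I error is 2Φ(−1.96/R). Example at 1,200 persons and s = 0.10: R = √(1 + 797 × 0.01) = 2.99 and 1.96/2.99 = 0.654, giving 51.3%.

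| Assumed s | 1,200 persons | 1,500 persons | Share of between-cluster log variance that district and baseline must explain |
|---|---|---|---|
| 0 | 5% | 5% | 100% |
| 0.02 | 8.8% | 9.7% | 99.8% |
| 0.05 | 25.7% | 29.4% | 98.5% |
| 0.10 | 51.3% | 55.4% | 93.8% |
| 0.25 | 78.3% | 80.5% | 61.5% |
| 0.42 | 86.9% | 88.3% | none |

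The last column uses the log SD implied by a CV of 0.42, √ln(1 + 0.42²) = 0.403. Type I error reaches 10% where R = 1.96/1.645, that is at s = 0.023 (1,200) or 0.021 (1,500). At 3,000 persons and s = 0.10 it is 67%.

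**4. Can baseline adjustment rescue the model?** Three months gives 0.332 × 0.25 × 1,200 = 100 cases, or 125 at 1,500, a log SD of 0.10 or 0.09. Suppose that true baseline rates carried every within-district difference, with variance v. Noise in the baseline still leaves residual variance v/(1 + vμ_b), where μ_b is the baseline count.
- v = 0.10²: residual SD 0.071 or 0.067, type I error 38% or 40%.
- v = 0.25²: residual SD 0.093 or 0.084, type I error 49% at both populations.

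**5. Simulation.** 1,000 null trials per setting, with the district-only Poisson mixed model and a baseline covariate.

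| s | 1,200 persons | 1,500 persons |
|---|---|---|
| near 0 | 4.2% | 4.3% |
| 0.05 | 29.4% | 32.1% |
| 0.10 | 52.1% | 56.8% |
| 0.25 | 79.3% | 82.7% |

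These agree with step 3 within Monte Carlo error of about 1.5 points and slightly larger simulated counts. On the same data for s = 0.05 to 0.25, adding a cluster random effect gave 5.5–6.8%. A paired regression of log rates on a t reference with 30 df gave 4.3–5.4%. The inflation therefore comes from the omitted term.

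**The case against.** The strongest reply is that the closing sentence of SAP 8.1.1 may be meant for every model in the subsection, including the primary one. If so, the cluster term is present and the inflation largely disappears. SAP 9.2 concerns covariates and says nothing about error structure, so it does not settle the matter alone.

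That reading fits the text poorly. The sentence comes straight after the secondary analyses and calls the district effect an addition still to be assessed, whereas the primary model already has one. If the sentence does cover the primary model, the section contradicts itself on whether district is in the model. The text has to change on either reading.

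Three further points stand as limits:
- The residual SD is assumed, and the percentages illustrate a range.
- The CV of 0.42 comes from 14 MRCs and mixes variation between and within districts. It shows that extra-Poisson variation was expected, not how much remains within pairs. The 0.42 row is an extreme bound.
- The gap concerns the 24-month primary analysis. The secondary incidence models and the survey models have cluster effects stated, although SAP 8.2.1 does not name net access in its model sentence.

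**Conclusion.** The concern holds. On its natural reading, SAP 8.1.1 tests the primary hypothesis with counting error as the only source of variation within a district. The type I error is 26–29% at a residual SD of 0.05 and 51–80% at 0.10 to 0.25.

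These figures are conditional on the district-only reading, model-based standard errors, the minimum target-area populations and the planned incidence. The conclusion is less sensitive than the figures. To keep the error below 10%, district and a three-month baseline would have to explain more than 99% of the between-cluster variance on which the trial was sized. Target areas above the minimum raise the error further. This is the trial's primary test, so the model must be corrected before analysis.

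**What to change.** In SAP 8.1.1, state one primary model that includes cluster-level variance:
- the Poisson model with a district effect, a cluster random effect and log baseline incidence (with one record per cluster, the cluster term is the extra-Poisson variance); or
- a paired regression of cluster log rates with district and log baseline, on a t reference. This held its level most closely in the simulation.

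If an overdispersion or robust variance is preferred, give its form and level. Replace the opening of the closing sentence with a list of the models it covers. Put the same structure in Protocol 13.5, and reword its statement about the level of randomisation to say that clusters are randomised within districts.

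The cost is wording in two documents and one model term, with no new data or participants. Confidence intervals widen to their proper width. Power follows from SE = √[(2s² + 1/μ + 1/(0.74μ))/32] and a noncentral t on 30 df. At 1,200 persons and s = 0.42, the SE is 0.105 against a log IRR of 0.301, giving about 79%. It is 97% at s = 0.30 and above 99% at 0.25.

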## 8.2 Secondary outcomes from cross-sectional surveys

Secondary outcomes from the 12 and 24 month cross-sectional surveys will include the following:

1. Prevalence of parasitemia in children 2-10 years of age - defined as the proportion of children with a positive thick blood smear by microscopy.
2. Prevalence of anemia in children 2-4 years of age - defined as the proportion of children with a hemoglobin level < 11 g/dL.
3. Measures of LLIN ownership, coverage and use defined as follows:
  - a. LLIN ownership - the proportion of households that owned at least one LLIN),
  - b. Adequate LLIN coverage - the proportion of households that owned at least one LLIN for every two residents.
  - c. LLIN access - proportion of residents who could sleep under a LLIN, if each LLIN in the household were used by up to two residents
  - d. LLIN use - the proportion of household residents who reported sleeping under an LLIN the previous night.

### 8.2.1 Analytical approach

All analyses will be conducted using an intention-to-treat approach according to the treatment allocations the clusters were randomized to. Separate analyses will be conducted for the 12 and 24 month cross-sectional surveys. We will compare individual level estimates of the prevalence of parasitemia and anemia between the intervention (PPF LLINs) and control arm (PBO LLINs) using a mixed effects logistic regression model with random effects at the level of the cluster and household. We will compare household level estimates of LLIN ownership, coverage, and use using a mixed effects logistic regression model with a random effect at the level of the cluster. Effects of the intervention will be expressed as odds ratios (odds in the intervention arm/odds in the control arm).

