1.8 LLINEUP trial

In 2017-18, the Ugandan Ministry of Health distributed LLINs with, and without, PBO through a national mass-distribution campaign, providing a unique opportunity to rigorously evaluate PBO LLINs across different epidemiological settings. In close collaboration with the Ministry of Health, we embedded a cluster-randomised trial to evaluate the impact of the LLINs delivered in the 2017-18 national campaign at an unprecedented scale in Eastern and Western Uganda. Overall, 104 clusters (health sub-districts) were included, covering 40% of Uganda (Figure 10) [38]. Proportionate randomisation was used to assign clusters to one of four arms, including LLINs with PBO (32 PermaNet 3·0, 20 Olyset Plus), and conventional LLINs (37 PermaNet 2·0, 15 Olyset Net). At baseline, 6, 12, 18 and 25 months after LLIN distribution, cross-sectional surveys were conducted in 50 randomly selected households per cluster (5,200 per survey); a sub-set of 10 households per cluster (1,040 per survey) were randomly selected for entomology surveys. The primary outcome was parasite prevalence by microscopy in children aged 2-10 years.

Baseline surveys were conducted in 2017 [4, 16, 17]. LLINs were delivered from March 2017 to March 2018. In the 'as treated' analysis, three clusters were excluded because no predominant LLIN was received, and four clusters were reassigned, resulting in 49 PBO LLIN (31 PermaNet 3·0, 18 Olyset Plus) and 52 non-PBO LLIN clusters (39 PermaNet 2·0, 13 Olyset Net). At six months, parasite prevalence was 10.7% in the PBO arm vs 14.5% in the non-PBO arm (prevalence ratio [PR] adjusted for baseline values 0.74, 95% CI: 0.62–0.87, $p<0.001$). Results were similar at 12 months (10.6% vs 13.0%, PR 0.73, 95% CI: 0.63–0.85, $p=0.001$) and at 18 months (11.8% vs 14.0%, PR 0.84, 95% CI: 0.72–0.98, $p=0.03$). In the 90 clusters for which follow-up data were available at 25 months (42 PBO vs 48 non-PBO), parasite prevalence remained lower in the PBO arm than the non-PBO arm (17.1% vs 19.8%, PR 0.80, 95% CI: 0.69–0.93, $p=0.005$). Although overall

[figure not shown]

Figure 10. Map of LLINEUP study sites. In total, 104 health sub-districts (clusters) from 48 districts were included.

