13.5 Analytical plan

All analyses will be conducted using an intention-to-treat approach. For our primary outcome, we will compare cluster level estimates of the incidence of malaria between intervention and control arms using a mixed effects Poisson regression model since randomization will occur at the district level (each district will include two clusters, randomized to the two study arms). We will also adjust our model for baseline estimates of malaria incidence (3 months prior to the intervention) and additional cluster-level covariates from the cross-sectional surveys including treatment seeking behaviour (to account for cases of malaria not captured at the MRCs) and the diagnostic accuracy of RDTs vs microscopy (to account for differences in the use of these diagnostic tests between clusters). The effect of the intervention will be expressed as an incidence rate ratio (incidence in the intervention arm/incidence in the control arm). Our primary analysis will evaluate malaria incidence over 24-months following the intervention. We will also perform secondary analyses of malaria incidence stratified by time following the intervention (year 1 vs year 2).

For our secondary outcomes, comparisons between intervention and control arms will be made using an individual-level approach to the analysis due to the large number of clusters per arm. Prevalence measures (parasitaemia, anaemia, LLIN ownership, LLIN coverage, LLIN access and LLIN use) will be compared using mixed effects logistic regression models with random effects at the level of the cluster and household. The effect of the intervention will be expressed as the prevalence ratio (prevalence in the intervention arm/prevalence in the control arm). For comparison of vector density, LLIN integrity, and bio-efficacy (funding permitting) between treatment arms, regression models will be used with generalized estimating equations to allow for within-cluster correlations. The effect of the intervention will be expressed as the density or rate ratio (density or rate in the intervention arm / density or rate in the control arm). Chemical analysis of withdrawn LLINs and their unused controls will be compared using the Wilcoxon rank sum test.

14 Ethical considerations

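### The parasitaemia and anaemia models omit the cluster baseline incidence that the primary model already uses, giving up precision that would cost almost nothing

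*SAP*

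**What the plan says.** For the 12- and 24-month surveys, SAP 8.2.1 models parasitaemia and anaemia "using a mixed effects logistic regression model with random effects at the level of the cluster and household". Arm is the only fixed effect implied. Protocol 13.5 agrees: prevalence outcomes "will be compared using mixed effects logistic regression models with random effects at the level of the cluster and household".

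The primary model is treated differently. SAP 8.1.1 specifies "adjustment for log-transformed estimates of the baseline malaria incidence (3 months prior to the intervention) for each cluster". SAP 9.2, the section on covariates, is confined to that outcome: "In the primary analysis of the primary outcome (malaria incidence) we will adjust for cluster level baseline estimates of malaria incidence". It lists nothing for the survey outcomes.

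No survey-based baseline is assured. Protocol 7.1 makes a baseline community survey conditional on resources. Protocol 7.4.6 reports funding for post-distribution surveys in 12 target areas only. Facility incidence is therefore the only pre-intervention malaria measure planned for all 64 clusters. It refers to the same target areas from which survey households are drawn.

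**The concern.** In a cluster trial with about 90 children per cluster, most of the error in a prevalence comparison comes from differences between clusters. Sampling more children hardly reduces it; explaining cluster differences with a pre-intervention measure does. The plan defines such a measure for every cluster and uses it for the primary outcome, but leaves it out of the survey models without giving a reason.

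What is at stake is the width of the intervals for secondary objective 1 (parasite prevalence and anaemia). There is also a question of timing. A covariate named in the SAP before the arms are compared is uncontroversial; the same covariate added afterwards would look chosen for its result.

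**Working it through.** **Inputs.** 32 clusters per arm (SAP 6.1). 50 × 1.8 = 90 children per cluster, CV k = 0.4, control prevalence 10–70%, 80% power, two-sided 5% (SAP 6.2). The correlation r between log baseline incidence and cluster prevalence is assumed. Anaemia is restricted to ages 2–4 (SAP 8.2). If children are spread evenly over the nine single years from 2 to 10, that gives 90 × 3/9 = 30 per cluster, also an assumption.

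**Formula** (unmatched cluster comparison of proportions, p1 = PR × p0):

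n = (1.96 + 0.84)² × [W + B] / (p0 − p1)², with W = [p0(1 − p0) + p1(1 − p1)]/m and B = k²(p0² + p1²).

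The version that adds 1 to n gives slightly stronger detectable effects (0.728 instead of 0.732 at 30%) and virtually the same power changes.

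**The plan's own figure.** SAP 6.2 states a detectable PR of 0.72–0.75. The formula gives 0.748 at 70% prevalence and 0.719 at 20%, which match. At 10% it gives about 0.685; power at PR 0.72 there is about 69%. That mismatch is a separate matter. It does mean power at low prevalence is below the stated 80%.

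**Without adjustment, 30% prevalence.** PR 0.732 gives p1 = 0.2196.
- W = (0.2100 + 0.1714)/90 = 0.00424
- B = 0.16 × (0.0900 + 0.0482) = 0.02212
- (p0 − p1)² = 0.0804² = 0.00646
- n = 7.85 × 0.02635/0.00646 = 32.0

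Between-cluster variation is 0.02212/0.02635 = 84% of the error variance. The same sum gives 58% at 10% prevalence and 96% at 70%.

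**With adjustment.** The covariate removes a fraction r² of B, so k becomes 0.4 × √(1 − r²). For r = 0.5: B = 0.75 × 0.02212 = 0.01659 and W + B = 0.02083. Power = Φ(√(32 × 0.00646/0.02083) − 1.96) = Φ(1.19) = 88%.

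Power is taken at the PR that has 80% power without adjustment: 0.732 at 30% prevalence, 0.685 at 10%, and 0.696 for anaemia at 30% prevalence with 30 children per cluster.

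| r (assumed) | k after adjustment | Detectable PR, 30% | Power, 30% | Power, 10% | Power, anaemia |
|---|---|---|---|---|---|
| 0 | 0.400 | 0.732 | 80% | 80% | 80% |
| 0.2 | 0.392 | 0.736 | 81% | 81% | 81% |
| 0.3 | 0.382 | 0.741 | 83% | 82% | 82% |
| 0.5 | 0.346 | 0.759 | 88% | 86% | 86% |
| 0.7 | 0.286 | 0.789 | 96% | 91% | 92% |

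**Check by cluster-level simulation** (3,000 trials per setting). At 30% prevalence the ratio of adjusted to unadjusted standard error is 0.97, 0.90 and 0.79 for r = 0.3, 0.5 and 0.7; power goes from 77 to 79%, 78 to 86% and 77 to 93%. At 10% prevalence the ratios are 0.99, 0.94 and 0.88. These gains are slightly below the formula's. At r = 0 the ratio is 1.008, a loss of less than 1 point of power.

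**The case against.** The strongest reply is that nothing here is an error. Randomised clusters compared without adjustment give a valid estimate, and SAP 6.2 sized the survey outcomes on the full CV of 0.4 without counting on a covariate. That stands. A reader might infer that the unadjusted comparison is biased because chance imbalance is left uncorrected. It is not: the interval already allows for such imbalance.

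The size of the gain is also open. The documents give no r and offer reasons to expect a modest one. The baseline is a 3-month window, and delivery runs in waves from November 2020 to March 2021 (SAP 3.1), so windows fall in different months in different clusters. The numerator is all-age cases seen at the facility, and SAP 8.1.1 itself expects cases missed there and differing use of RDTs and microscopy. The outcome is microscopy in children 12 or 24 months later. These points stand, and a substantial gain cannot be claimed as fact.

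Two further inferences should be resisted:
- **That a usable baseline is already in hand everywhere.** The accurate population denominator comes from a census run with the 12-month survey (protocol 4.1). Both Moyo facilities started in September 2020 (protocol Table 2), so a full 3 months there needs nets to have arrived in December 2020 or later. The primary model has the same limits and accepts them.
- **That the predecessor trial sets a direct precedent.** Its result is reported as a "prevalence ratio [PR] adjusted for baseline values 0.74" (protocol 1.8). Parasite prevalence was its own surveyed outcome and it ran baseline surveys, so this appears to be adjustment for that outcome at baseline, not for a facility-based proxy.

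Finally, the formula ignores the pairing of clusters by district. If district is also modelled, only the within-district part of the correlation helps, so the gains above cannot simply be added to those from a district effect.

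**Conclusion.** The concern holds as a worthwhile improvement to a valid analysis of secondary outcomes. The survey models omit a baseline covariate that the SAP already defines for each cluster. Adding it risks less than 1 point of power. If r is about 0.2–0.3 the gain is only 1 to 3 points; it becomes material (6 to 8 points for parasitaemia at 10–30% prevalence) at r = 0.5 and larger beyond that.

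These figures rest on an assumed r, a CV of 0.4 for both outcomes, an assumed 30 children per cluster for anaemia, an unmatched formula and the prevalence-ratio scale, whereas SAP 8.2.1 reports odds ratios. Nothing in the documents shows that r is the same for anaemia as for parasitaemia. Confidence is moderate.

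**What to change.** In SAP 8.2.1 and 9.2, state that the main 12- and 24-month models for parasitaemia and anaemia include log baseline malaria incidence, the same variable as in SAP 8.1.1, as a cluster-level fixed covariate, and that the unadjusted estimate is shown beside it. Align protocol 13.5. State how a baseline shorter than 3 months is handled, with the same rule as in the primary model.

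No child-level covariate such as age is proposed. The documents give no basis for sizing its benefit, and it would change the conditional odds ratio being estimated.

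The cost is a sentence or two in the SAP and one degree of freedom, with no new data. Because the trial is open-label, the change should be dated before survey outcomes are compared by arm.
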